6.3 PATIENT SETS ANALYSED

Enrolled set (ES)

The enrolled set consists of all patients who signed informed consent and fulfilled all eligibility criteria.

Treated set (TS)

Treated Set (TS) includes all patients from ES and who were dispensed medication and are documented to have taken at least one dose of first-line treatment afatinib.

6.5 POOLING OF CENTRES

This section is not applicable because there will be no pooling of centres or countries and no modelling thereof.

6.6 HANDLING OF MISSING DATA AND OUTLIERS

The details of imputation for partial and missing data for date of adverse event and concomitant therapy are stated at [section 7.10.1](#) and [7.2](#) below, respectively. The details of imputation for partial and missing data for date of TOT event and OS event are stated at [section 7.6](#) and [7.7.1](#) below, respectively. Other missing data will be recorded as missing/unknown, and no other imputation of missing data will be performed unless otherwise stated.

6.7 BASELINE, TIME WINDOWS AND CALCULATED VISITS

Unless otherwise specified, ‘Baseline’ values are defined as the last non-missing value prior to first administration of Afatinib.

The time window is 28 -7/+2 days for subsequent clinic visits during first-line treatment period, first visit \leqslant 1 month followed by regular visits according to institution standards after start of second line treatment, regular visits according to institution standards after start further subsequent treatments.

‘Study Day’ will be calculated relative to the date of first administration of Afatinib.

Proprietary confidential information © 2024 Boehringer Ingelheim International GmbH or one or more of its affiliated companies

- Study Day = Assessment Date – Date of first administration of Afatinib for visit (or event) prior to first study treatment.
- Study Day = Assessment Date – Date of first administration of Afatinib + 1 day for visit (or event) at or after first study treatment.

7. PLANNED ANALYSIS

Continuous data will be summarized in terms of the mean, standard deviation, median, minimum, maximum and number of observations, unless otherwise stated. The minimum and maximum will be reported to the same number of decimal places as the raw data recorded in the database. The mean, median will be reported to one more decimal place than the raw data recorded in the database. The standard deviation will be reported to two more decimal places than the raw data recorded in the database. In general, the maximum number of decimal places reported shall be four for any summary statistic.

Categorical data will be summarized in terms of the number of subjects providing data at the relevant time point (n), frequency counts and percentages. Percentages will be presented to one decimal place. Percentages will not be presented for zero counts. The category missing will be displayed only if there are actually missing values. When necessary, continuous variables also will be categorized into intervals, with the distribution of patients (n, N, %) for each interval provided.

Confidence intervals will be presented to one more decimal place than the raw data.

Raw data collected in eCRF will also be listed.

7.1 DEMOGRAPHIC AND OTHER BASELINE CHARACTERISTICS

Only descriptive statistics are planned for this section of the report. Demographic and baseline characteristic parameters collected and to be presented include:

- Age [years]
- Age class (<65, ≥ 65 years)
- Gender (Male, Female)
- Race (as defined in the eCRF)
- Height [cm]
- Weight [kg]
- Body mass index (BMI) [kg/m^2] (defined as weight [kg]/(height [cm]/100)²)
- Smoking status (Former, Current, Never)
- Baseline ECOG score
- EGFR mutation type
- Comorbidity history
- Surgery history
- Tumor histology classification
- Disease stage at the start of afatinib

Proprietary confidential information © 2024 Boehringer Ingelheim International GmbH or one or more of its affiliated companies

- Metastases at the start of afatinib
- Afatinib starting dose at baseline
- Medical history
- Prior therapy

In addition, to assess the presence of channeling bias, the data from study 1200-0066 will be used to assess potential channeling and to put the results into perspective. The baseline characteristics listed above (Except for Race) in this study and in study 1200-0066 will be presented separately. Patient characteristics will be compared between the two studies using absolute standardized differences (ASD), where an ASD of at least 10% will be considered a meaningful difference.

For continuous variable:

$$ASD = \frac{|(mean_1 - mean_2)|}{\sqrt{(s_1^2 + s_2^2)/2}}$$

- $mean_1$ is the arithmetic average of the analysed variable for study 1200-0318.
- $mean_2$ is the arithmetic average of the analysed variable for study 1200-0066.
- s_1 is the standard deviation of the analysed variable for study 1200-0318.
- s_2 is the standard deviation of the analysed variable for study 1200-0066.

For binary categorical variable:

$$ASD = \frac{|(p_1 - p_2)|}{\sqrt{(p_1(1 - p_1) + p_2(1 - p_2))/2}}$$

- p_1 is the rate of the analysed variable for study 1200-0318.
- p_2 is the rate of the analysed variable for study 1200-0066.

For categorical baseline variables with levels, Dalton (2008) proposed to use a multivariate Mahalanobis distance method to generalize the standardized difference metric to handle a multinomial sample [\[3\]](#):

$$T = (p_{12}, p_{13}, \dots, p_{1k})'$$

$$C = (p_{22}, p_{23}, \dots, p_{2k})'$$

$$p_{jk} = Pr(\text{category } k \mid \text{treatment group } j), j \in \{1, 2\}, \text{ and } k \in \{2, 3, \dots, k\}$$

$$ASD = \sqrt{(T - C)'S^{-1}(T - C)}$$

Where S is a $(k-1) \times (k-1)$ covariance matrix defined as:

$$S = [S_{kl}] = \begin{cases} \frac{[p_{1k}(1 - p_{1k}) + p_{2k}(1 - p_{2k})]}{2}, & k = l \\ \frac{[p_{1k}p_{1l} + p_{2k}p_{2l}]}{2}, & k \neq l \end{cases}$$

Proprietary confidential information © 2024 Boehringer Ingelheim International GmbH or one or more of its affiliated companies

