9.5 STUDY SIZE

Seventy-six patients will be included in this study.

Based on LUX-Lung trials, we assume the median time on treatment (TOT) on afatinib to be 12 months in this study. Assuming that the time on treatment (TOT) follows an exponential distribution, it is expected to have 35 events till 2 years after last patient in, given total sample size equal to 76, considering a 30% drop out rate.

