9.9.3 Study Sample Size

76 patients were enrolled in this study, this is a small sample size which may impact the assessment of study outcomes. A sample size of 76 patients is expected to ensure an 80% chance to observe the width of the 90% CI of median TOT of afatinib smaller than or equal to 11 months.

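### With 76 patients the 10% ASD marker lies within sampling error, so a flag against study 1200-0066 cannot by itself show channelling

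*SAP*

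**What the plan says.** SAP 7.1 states that "the data from study 1200-0066 will be used to assess potential channeling and to put the results into perspective". On presentation it says: "The baseline characteristics listed above (Except for Race) in this study and in study 1200-0066 will be presented separately". The two studies are then compared by ASD, "where an ASD of at least 10% will be considered a meaningful difference"; protocol 9.7 carries the same rule. SAP 7.1 gives one formula for continuous and one for binary variables. For variables with more levels it cites a source that "proposed to use a multivariate Mahalanobis distance method to generalize the standardized difference metric to handle a multinomial sample". The 10% value is the only threshold given, whatever the number of levels.

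The section opens with the statement "Only descriptive statistics are planned for this section of the report". SAP 7.4 and protocol 9.9.2 go further: they say the comparison allows the study to verify whether a safety or efficacy difference is due to baseline characteristics or to the sequential therapy. SAP 7.5 marks methods for confounding as not applicable.

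On size, protocol 9.5 says "Seventy-six patients will be included in this study", and protocol 9.9.3 concedes that "this is a small sample size which may impact the assessment of study outcomes". That remark is about study outcomes and the width of the interval for median time on treatment; it does not reach the ASD. Neither document gives the size of 1200-0066, a confidence interval for the ASD, or a rule for how many flags would indicate channelling.

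**The concern.** Channelling is a prescribing mechanism, so the question is whether the populations behind the two studies differ. An observed ASD reflects both a population difference and chance. If 10% is smaller than the ordinary chance variation of the ASD at this sample size, the report will probably list several meaningful differences even if no channelling took place, and nothing in the plan lets a reader tell these from real ones. SAP 7.4 and protocol 9.9.2 would then rest an explanation of safety or efficacy differences on a comparison that cannot carry it.

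**Working it through.** The plan gives no standard error or chance-flag rate for the ASD, so there is no figure of its own to reproduce.

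**Inputs**
- Threshold: 0.10 (SAP 7.1, protocol 9.7).
- n1 = 76 (protocol 9.5). A smaller Treated Set would raise the rates below.
- n2, the size of 1200-0066: not given. Assumed range 76 to infinity; infinity is the case most favourable to the rule.
- Characteristics compared: SAP 7.1 lists 18, and leaving out race gives 17.
- Number of levels: stated for few variables. One example is "Smoking status (Former, Current, Never"), with three levels.

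**Standard error with identical populations**

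SE ≈ sqrt(1/n1 + 1/n2).
- n2 infinite: sqrt(1/76) = 0.115
- n2 = 500: 0.123
- n2 = 200: 0.135
- n2 = 76: sqrt(2/76) = 0.162

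All exceed 0.10.

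**Chance of an ASD of at least 10%**

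For a continuous or binary variable (one degree of freedom), P = 2 × [1 − Φ(0.10/SE)]. With n2 infinite, 0.10/0.1147 = 0.872 and P = 38.3%. For k levels, ASD²/SE² is approximately chi-square with k − 1 degrees of freedom, so P = P(χ² ≥ (0.10/SE)²).

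| n2 | Continuous or binary | 3 levels | 4 levels |
|---|---|---|---|
| infinite | 38.3% | 68.4% | 85.9% |
| 500 | 41.7% | 71.9% | 88.3% |
| 200 | 45.8% | 75.9% | 90.8% |
| 76 | 53.8% | 82.7% | 94.4% |

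**Checks on the approximations**
- Exact binomial enumeration with the SAP's binary formula, prevalences 5–50%, gives minimum rates of 41.6% (n2 = 500), 45.9% (n2 = 200) and 52.0% (n2 = 76). Against a fixed, error-free reference it gives 35–44%.
- Very rare items can fall well below this. At an assumed prevalence of 0.1% against a fixed reference, the chance of no case in 76 is 0.999^76 = 0.927. The ASD is then 0.001/sqrt(0.000999/2) = 0.045, which is not flagged, so the flag rate is at most about 7%.
- Multinomial simulation with n2 from 200 to very large gives 68–76% for three levels and 86–91% for four. It uses a covariance matrix with negative off-diagonal terms. The matrix in SAP 7.1 reads with positive ones, possibly a sign lost in conversion. With that sign the three-level rates are 70–79%, so the conclusion does not depend on it.

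**Expected number of flags**

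17 × 0.383 = 6.5 if every item had one degree of freedom and the comparator were infinitely large; 17 × 0.538 = 9.1 with n2 = 76. Multi-level items add to this. Correlation among items (age and age class; height, weight and BMI) makes flags cluster but does not change the expected number.

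**Size of ASD that chance produces (95th percentile with identical populations)**
- One degree of freedom, 1.96 × SE: 0.22 (n2 infinite) to 0.32 (n2 = 76).
- Three levels, sqrt(5.99) × SE: 0.28 to 0.40.
- Four levels, sqrt(7.81) × SE: 0.32 to 0.45.

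For 0.10 itself to be that 95% bound with equal study sizes, 1.96 × sqrt(2/n) = 0.10 gives n = 2 × 19.6² ≈ 768 per study.

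**The case against.** The ASD measures the size of an imbalance and is not a significance test, so a false-positive rate is not what it is designed around. SAP 7.1 calls the section descriptive, and protocol 9.1 says there are no comparisons between groups. No rule turns flags into a finding of channelling, and no flag triggers an adjustment. Both studies' characteristics are also shown separately, so readers see more than the flag. For putting results into perspective, an observed imbalance is relevant even if it arose by chance.

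Much of this stands, and it is why the 10% value may remain as a descriptive marker. It does not remove the point. SAP 7.1 gives assessing the presence of channelling as the purpose, and SAP 7.4 and protocol 9.9.2 claim that the comparison can verify the source of a difference. Those are conclusions beyond the sample.

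A reader might infer that the threshold should be replaced by a strict one, calling a difference meaningful only if the lower 95% limit exceeds 10%. That does not follow. It would require an observed ASD of 0.10 + 1.96 × SE, or 0.325 to 0.418 for one degree of freedom. The chance of flagging a true ASD of 0.30 would fall from 90–96% under the present rule to 23–41%. In a screen for bias, missing a real difference may be the costlier error.

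A reader might also infer that the plan uses the ASD as a formal test, or that covariates balanced in the sample would be flagged. Neither is so: there is no decision rule, and a covariate balanced in the sample has an ASD of zero. The rates above concern identical underlying populations.

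**Conclusion.** The concern holds as a weakness of calibration and interpretation. At 76 patients a 10% ASD is less than one standard error for continuous and binary variables, for any size of 1200-0066. With identical populations about 38–54% of these variables, 68–83% of three-level and 86–94% of four-level variables would be flagged, giving 6 or 7 or more flags among 17 characteristics. A flag alone therefore cannot show channelling, and the comparison cannot verify why a safety or efficacy difference arose.

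This rests on large-sample approximations, on 76 analysed patients, and on an assumed comparator size of 76 upwards. The 38% is an approximate floor, not a strict one: binary items vary by a few points around it, and very rare ones can be flagged less often.

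A reader might infer that the main results are compromised. The documents do not support that: the analyses of time on treatment, overall survival, response and safety make no use of the ASD.

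**What to change.** In SAP 7.1 and protocol 9.7:
- Keep the ASD, and keep 10% as a descriptive marker of observed imbalance.
- Report each ASD with a 95% confidence interval.
- Beside it, show the value expected by chance with identical populations: 1.96 × sqrt(1/n1 + 1/n2) for continuous and binary variables (about 0.22–0.32), and the 95th percentile of the null distance for multi-level variables (about 0.28–0.40 for three levels, 0.32–0.45 for four). Compute these from the actual sizes of both analysis sets, and state the size of 1200-0066.
- State that ASDs between 10% and that value cannot be told from chance and are inconclusive about channelling.

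In SAP 7.4 and protocol 9.9.2, replace the claim to verify with wording the comparison can support, for example that it describes how the two samples differ at baseline. Do not adopt a rule that requires the lower 95% limit to exceed 10%.

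The cost is a few lines of text and one or two table columns, with no new data. Under protocol 10.1 a change to the protocol text needs approval as an amendment. Some differences will be labelled inconclusive, which is what 76 patients can support.

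### The multi-level ASD formula in SAP 7.1 has the wrong sign on its off-diagonal covariance terms, so its result depends on the reference category and can fall on the wrong side of the 10% threshold

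*SAP*

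**What the plan says.** SAP 7.1 compares baseline characteristics between this study and study 1200-0066 to look for channelling bias, and states that "an ASD of at least 10% will be considered a meaningful difference". It gives three formulas: one for continuous variables, one for binary variables, and one for variables with more levels. For the third it proposes "to use a multivariate Mahalanobis distance method to generalize the standardized difference metric" and takes ASD = sqrt((T - C)' S^-1 (T - C)).

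T and C hold the category proportions from category 2 onwards, so category 1 is the omitted reference. No rule says which level is category 1.

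S is a "covariance matrix defined as" follows:

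- diagonal (k = l): half of "p_{1k}(1 - p_{1k}) + p_{2k}(1 - p_{2k})", the average of the two multinomial variances;
- off-diagonal (k ≠ l): half of "p_{1k}p_{1l} + p_{2k}p_{2l}", with no minus sign in front.

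The SAP history table (section 10) records that this method was added in V1.1. Neither document gives a different version of the formula.

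**The concern.** A patient falls in one category only, so the indicators of two different categories are negatively correlated. A covariance matrix for them needs negative off-diagonal entries, and the SAP prints positive ones. Two consequences follow. The value is wrong in general. It also changes with the level coded as category 1, which a valid Mahalanobis distance on these proportions cannot do.

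The formula covers every listed variable with three or more levels. "Smoking status (Former, Current, Never)" is one by its own description. ECOG score, EGFR mutation type, histology and disease stage are others if they are tabulated with three or more levels.

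The ASD with its 10% cut-off is the plan's only quantitative tool for channelling bias (Protocol 9.7, 9.9.2 and 9.11; SAP 7.1 and 7.4), and SAP 7.5 plans no adjustment for confounding. SAP 7.4 goes further and expects the comparison to separate the effect of baseline characteristics from that of treatment. An index that moves with an arbitrary coding order cannot support that reading.

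**Working it through.** **Inputs.** The formulas and the 10% threshold come from SAP 7.1. Neither document gives category proportions for either study, so all proportions below are assumptions chosen for illustration. The documents state no ASD value, so there is no plan figure to reproduce.

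**Sign of the covariance.** For indicators I_k and I_l with k ≠ l, the product I_k·I_l is always 0. Hence Cov(I_k, I_l) = 0 - p_k·p_l = -p_k·p_l. A simulated multinomial with p = (0.2, 0.3, 0.5) gave off-diagonals of -0.060, -0.101 and -0.149, against the theoretical -0.06, -0.10 and -0.15. The off-diagonal of S should therefore be -(p1k·p1l + p2k·p2l)/2.

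**Check on two levels.** S is then a single number with no off-diagonal, and both versions equal the SAP's binary formula: 0.40 against 0.50 gives 0.10 / sqrt((0.24 + 0.25)/2) = 0.202. The error starts at three levels.

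**Three levels in general.** Write d1 and d2 for the differences in the two retained categories, a and b for the diagonal entries, and c for the off-diagonal entry. Then

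ASD² = (b·d1² + a·d2² - 2·c·d1·d2) / (a·b - c²).

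Reversing the sign of c changes only the cross term. The printed and correct values agree only when that term vanishes, that is, when a retained category has the same proportion in both studies.

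**Missed imbalance.** (0.10, 0.50, 0.40) against (0.15, 0.475, 0.375), category 1 omitted:

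- d1 = d2 = 0.025
- a = (0.25 + 0.249375)/2 = 0.2496875
- b = (0.24 + 0.234375)/2 = 0.2371875
- size of c = (0.20 + 0.178125)/2 = 0.1890625
- a·b - c² = 0.0592228 - 0.0357446 = 0.0234782
- as printed: 0.000625 × (0.486875 - 0.378125) / 0.0234782 = 0.00289, ASD = 0.054
- with the minus sign: 0.000625 × (0.486875 + 0.378125) / 0.0234782 = 0.02303, ASD = 0.152

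**False alarm.** (0.45, 0.45, 0.10) against (0.48, 0.42, 0.10), category 3 omitted:

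- d1 = -0.03, d2 = 0.03
- a = 0.24855, b = 0.24555, size of c = 0.20205
- a·b - c² = 0.0202073
- as printed: 0.0009 × (0.4941 + 0.4041) / 0.0202073 = 0.0400, ASD = 0.200
- with the minus sign: 0.0009 × (0.4941 - 0.4041) / 0.0202073 = 0.0040, ASD = 0.063

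**Each category in turn as reference.**

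| Study 1 | Study 2 | Printed, category 1 / 2 / 3 omitted | Correct, any reference |
|---|---|---|---|
| 0.10, 0.50, 0.40 | 0.15, 0.475, 0.375 | 0.054 / 0.182 / 0.190 | 0.152 |
| 0.60, 0.22, 0.18 | 0.66, 0.19, 0.15 | 0.099 / 0.225 / 0.243 | 0.125 |
| 0.20, 0.10, 0.70 | 0.23, 0.12, 0.65 | 0.174 / 0.257 / 0.089 | 0.1075 |
| 0.45, 0.45, 0.10 | 0.48, 0.42, 0.10 | 0.063 / 0.063 / 0.200 | 0.063 |
| 0.33, 0.33, 0.34 | 0.30, 0.36, 0.34 | 0.074 / 0.074 / 0.127 | 0.074 |
| 0.10, 0.45, 0.45 | 0.20, 0.40, 0.40 | 0.108 / 0.356 / 0.356 | 0.283 |
| 0.05, 0.475, 0.475 | 0.05, 0.525, 0.425 | 0.459 / 0.103 / 0.103 | 0.103 |

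In the first three rows a difference above 10% can be missed. In the next two a difference below 10% can be flagged. In the last two the classification stays the same but the size is wrong.

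**How often.** Simulated with 76 patients in this study (Protocol 9.5), an assumed 300 in study 1200-0066 (its size is not given) and equal true proportions. The printed value depended on the reference in every draw. The 10% classification was wrong for at least one choice of reference in about 33% of three-level and 19% of four-level draws. For any one fixed reference it was wrong in about 13% and 7%. The ratio of printed to correct ASD ran from about 0.60 to 2.30 (5th to 95th percentile) with three levels, and from 0.64 to 1.71 with four.

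**The case against.** **Extraction.** The text was machine-read from a PDF, and a leading minus before a bracket is easier to lose than one between two symbols. This cannot be fully excluded. The other minus signs in the same block did survive, and a look at the source PDF settles it.

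**The program may be right.** No program or computed ASD is available, and a programmer who followed the named method rather than the printed formula would get correct values. That stands, so the harm is conditional on programming as printed. But SAP section 3 says the document outlines the programming specifications, and the reference cited for the method is listed as unpublished, so a validator has little else to check against.

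**Misclassification is modest and the flag is noisy anyway.** A real program fixes one reference, so 13% and 7% are fairer figures than 33% and 19%. Under the same simulation assumptions the correct ASD already reaches 10% by chance in about 74% of three-level and 89% of four-level draws. This is a fair limit on what the flag can say, but it does not justify computing it wrongly.

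**Descriptive role.** The comparison feeds no adjustment, weighting or exclusion, and the two studies' distributions are also shown separately. This limits the consequences. The reported values and the 10% flags would still be wrong.

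**Conclusion.** The concern holds. By the SAP's own description of S, the off-diagonal sign is wrong. This is algebra and rests on no assumed figure, and neither does the dependence on the reference level. The size of the error and how often 10% is crossed do depend on the assumed proportions and, for the frequencies, on the assumed 300 patients in study 1200-0066. In the examples the printed formula turns 0.152 into 0.054 and 0.063 into 0.200, so it can err in both directions.

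The reach is limited to baseline variables with three or more levels in the comparison with study 1200-0066. Only smoking status is documented as such a variable. The continuous and binary ASDs, TOT, OS, ORR and safety results are not touched.

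**What to change.** In SAP 7.1, change the k ≠ l entry of S to -(p1k·p1l + p2k·p2l)/2, after comparing with the source PDF in case the sign was lost in reading. In the ASD program, rerun each multi-level variable with every category in turn as the reference and confirm that the value does not change; this test catches the error without any external reference. If any ASD tables were produced with the printed sign, regenerate them.

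The cost is one character in the SAP, a history-table entry and a short program check. No data collection or other analysis changes.
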